## 9. SELECTION AND ENROLLMENT OF SUBJECTS

### 9.1. Inclusion Criteria and Exclusion Criteria

#### 9.1.1. Inclusion Criteria:

Subjects meeting all the following criteria may be included in the study:

1. Male or female subjects between 18-80 years of age, inclusive.
2. Subjects have a diagnosis of possible, probable or definite ALS in accordance with the Revisited El-Escorial Criteria
3. Subjects must be currently on an oral diet and able to take foods and liquids by mouth equivalent to a score of 4 or above on the Functional Oral Intake Scale (Crary, 2005).
4. Subjects must have no known allergy to barium sulfate or Metformin.

---

#### CONFIDENTIAL INFORMATION

The information in this study protocol is confidential. Any disclosure, copying or distribution of the information contained within is strictly prohibited without written consent from University of Florida.

5. Subjects or subject's legally authorized representative must be willing and able to complete informed consent/assent and HIPAA authorization.
6. Ability to comprehend and be informed of the nature of the study, as assessed by the PI or Sub-Investigator.
7. Availability to participate for the entire study duration.
8. Female subjects of childbearing potential must have a negative urine pregnancy test at Screening and Visit 1, 3, and 4.

#### **9.1.2. Exclusion Criteria:**

Potential subjects meeting any of the following criteria will be excluded:

1. Subjects who score 3 or below on the Functional Oral Intake Scale (Crary, 2005).
2. Subjects who do not carry the C9orf72 hexanucleotide repeat expansion as determined by previous laboratory analysis.
3. Subjects with known allergy to barium sulfate or Metformin.
4. Subjects with a history of clinically significant liver disease, renal disease, or any other medical condition judged to be exclusionary by the investigator.
5. Subjects who are unwilling to sign informed consent or subjects who for any other reason in the judgment of investigator are unable to complete the study.
6. Female subjects who have a positive urine pregnancy test ( $\beta$ hCG) at screening or visit 1, 2, 3, and 4, or are trying to become pregnant or are breastfeeding.
7. Subjects with active cancer within the previous 2 years, except treated basal cell carcinoma of the skin.
8. Subjects who have taken any experimental drug within 30 days prior to enrollment or within 5 half-lives of the investigational drug – whichever is the longer period.
9. Subjects with known history or presence of moderate or severe renal impairment as defined by an eGFR value below 30 mL/min/1.73 m^2.
10. Subjects with hepatic impairment as defined by baseline elevations of serum aminotransferases greater than 5 times upper limit of normal or evidence of liver dysfunction (e.g., elevated bilirubin).
11. Use of potentially hepatotoxic drugs: (e.g., allopurinol, methyldopa, sulfasalazine).
12. Subjects with clinically significant abnormal laboratory values in the judgment of the investigator.

---

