#### Elimination

Renal clearance is approximately 3.5 times greater than creatinine clearance, which indicates that tubular secretion is the major route of metformin elimination. Following oral administration, approximately 90% of the absorbed drug is eliminated via the renal route within the first 24 hours, with a plasma elimination half-life of approximately 6.2 hours. In blood, the elimination halflife is approximately 17.6 hours, suggesting that the erythrocyte mass may be a compartment of distribution.

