## 6.4. Safety

Metformin is contraindicated in patients with severe renal impairment (eGFR below 30 mL/min/1.73 m^2), hypersensitivity to Metformin, and acute or chronic metabolic acidosis, including diabetic ketoacidosis, with or without coma.

See attached product information sheet (Appendix H) regarding the warnings and precautions (lactic acidosis, vitamin B12 deficiency, and hypoglycemia).

The most commonly observed AEs associated with the use of Metformin are listed in table 1 of the product information sheet and include diarrhea, nausea/vomiting, flatulence, asthenia, indigestion, abdominal discomfort, and headache. Diarrhea lead to discontinuation in 6% of patients.

Postmarketing experience has identified cholestatic, hepatocellular, and mixed hepatocellular liver injury (see package insert attached).

---

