#### **CONFIDENTIAL INFORMATION**

The information in this study protocol is confidential. Any disclosure, copying or distribution of the information contained within is strictly prohibited without written consent from University of Florida.

13. Subject with implanted electrical device (i.e. cardiac pacemaker or a neurostimulator), metal or metallic clip(s) in their body (i.e., an aneurysm clip in the brain) that will be damaged by participation in the MRI portion of the study.
14. Anything else that, in the opinion of the investigator, would place the subject at increased risk or preclude the subject's full compliance with or completion of the study.

Inclusion in the study is entirely voluntary and subjects may withdraw at any time for any reason. Possible reasons for withdrawal could include serious adverse events, adverse events, and subject's choice. Subjects wishing to stop medication will immediately discontinue medication. Subjects who elect to discontinue medication will be asked to comply with end of study assessments (visit 4 on Table 3 - Schedule of Activities table) at a follow-up visit in an outpatient setting (to be determined by Investigator or Staff) at 14 +/- days after the last treatment Visit. Subjects who withdraw due to an adverse event will be followed whenever possible until resolution of the adverse event. It may be appropriate for the subject to return to the site 2 weeks after the subject is off study to evaluate for resolution of any adverse events and to receive further information about options for future clinical care. The Investigator will decide the course of action.

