## 10. DRUG PRODUCT

### 10.1. Drug Information

**Table 2 Drug Information**

Treatment	
Drug Name	Metformin SR
Strength	500mg
Dosage Form	Oral tablet
Manufacturer	
Dose	1 x 500 mg/day during week 1 2 x 500 mg/day during week 2 3 x 500 mg/day during week 3 4 x 500 mg/day during weeks 4-24 4 x 500 mg/day during Weeks 24-Week 36 (Optional dosing)

---

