### **11.2.2. Prohibited Medications/Interventions**

Concomitant medications and interventions will be reviewed at screening. The investigator may choose to exclude a subject from participation if a concomitant medication or intervention is judged likely to interfere with the study objectives or to affect the subject's safety.

The following drugs are known to interact with Metformin tablets (US Package Insert; revision 05/2018) and should not be administered with Metformin:

- Agents that may increase Metformin blood concentration;
- Agents that may decrease Metformin plasma concentrations;
- Agents that may increase the risk of lactic acidosis; Carbonic anhydrase inhibitors may increase risk of lactic acidosis.
- Agents that may impact glucose control and cause hyper or hypo glycemia; Taking Metformin with other drugs that lower blood sugar can raise your risk of hypoglycemia (low blood sugar).
- Potentially hepatotoxic drugs: (e.g., allopurinol, methyldopa, sulfasalazine)
- Drugs that reduce metformin clearance (such as ranolazine, vandetanib, dolutegravir, and cimetidine) may increase the accumulation of metformin.
- Medications that interact with Metformin include digoxin, cimetidine, furosemide, nifedipine, amiloride, ranitidine, triamterene, morphine, quinidine, vancomycin, trimethoprim and procainamide.
- Alcohol can potentiate the effect of metformin on lactate metabolism and should not be used in excess while taking Metformin.

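### Exclusion 9 says it bars moderate as well as severe renal impairment, but its only cut, eGFR below 30, is the one Section 6.4 gives for severe impairment alone

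*Combined protocol and SAP*

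**What the plan says.** Exclusion 9 in Section 9.1.2, with the same wording in the Synopsis, bars subjects with "known history or presence of moderate or severe renal impairment as defined by an eGFR value below 30 mL/min/1.73" m². Section 6.4 uses the same figure for one category only: "Metformin is contraindicated in patients with severe renal impairment (eGFR below 30 mL/min/1.73" m²). The visible text gives no other eGFR value and does not define moderate impairment.

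Three further items in Section 9.1.2 could reach a subject with reduced renal function:

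- Item 4: "Subjects with a history of clinically significant liver disease, renal disease, or any other medical condition judged to be exclusionary by the investigator".
- Item 12: "Subjects with clinically significant abnormal laboratory values in the judgment of the investigator".
- Item 14: "Anything else that, in the opinion of the investigator, would place the subject at increased risk".

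None of them states a renal value.

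On exposure, Section 10.1, Table 2 sets the maintenance dose at "4 x 500 mg/day during weeks 4-24" after weekly 500 mg steps, and the visible text has no renal dose rule. Under Elimination, Section 6.3 reports that "approximately 90% of the absorbed drug is eliminated via the renal route within the first 24 hours". Section 11.2.2 warns: "Drugs that reduce metformin clearance (such as ranolazine, vandetanib, dolutegravir, and cimetidine) may increase the accumulation of metformin".

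**The concern.** The criterion names two groups and supplies one number, and that number defines only one of them. A screener who follows the number admits a subject whom the words exclude. A screener who follows the words has no value to apply. Two people could reach opposite decisions on the same candidate and cite the same line.

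This is a mandatory safety criterion in a trial whose primary objective is safety and tolerability, and it concerns the main route by which the study drug leaves the body. Section 11.2.2 guards against clearance lowered by other drugs, while the numeric entry rule admits the group with lowered renal function that the criterion says it keeps out. A report that repeated Exclusion 9 would also describe the population as free of moderate impairment when the rule as applied did not ensure that.

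**Working it through.** No sample size, power or error-rate figure is involved. The check compares the two statements of the cut.

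**Inputs**

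| Place | Category named | eGFR cut (mL/min/1.73 m²) |
|---|---|---|
| Exclusion 9, Section 9.1.2 | moderate or severe | below 30 |
| Exclusion 9, Synopsis | moderate or severe | below 30 |
| Section 6.4 | severe | below 30 |
| Exclusions 4, 12 and 14 | investigator judgment | none given |

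**Step 1. Whom Exclusion 9 removes.** Those with eGFR below 30, now or by known history.

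**Step 2. Whom the severe category contains.** By Section 6.4, those with eGFR below 30.

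**Step 3. What 'moderate' adds.** {eGFR < 30} minus {eGFR < 30} is the empty set. The word adds no one.

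**Step 4. Where moderate impairment lies.** Moderate is less impaired than severe, and severe is everything below 30, so moderate must start at 30 or above. Exclusion 9 then shares no eGFR value with the moderate category. For example, a candidate at 35 with no known value below 30 passes.

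**Step 5. What else could exclude that candidate.** Exclusion 4 can be read as mandatory once renal disease is judged clinically significant, but it does not say at what eGFR that is so. Exclusions 12 and 14 rest on the investigator's judgment or opinion. All three can remove the candidate; none requires it at a stated value.

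**Step 6. Width of the gap.** The documents give no upper bound U for moderate impairment. I assume a range for U of about 45 to 60. The band that is named as excluded but numerically admitted runs from 30 up to U:

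- U = 45: 45 − 30 = 15 units wide.
- U = 60: 60 − 30 = 30 units wide.

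Steps 1 to 5 do not depend on this assumption; only the width in step 6 does.

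**The case against.** The strongest reply is that the number governs. The criterion gives an explicit definition, the Synopsis and Section 9.1.2 agree on it, and it equals the contraindication in Section 6.4, which is the only visible evidence of the intended cut. On that view the label is loose and the rule is clear. Renal risk at or above 30 is then left to Exclusions 4, 12 and 14 and to the investigator's review of all criteria and safety laboratory results before baseline is scheduled (Section 12.2.1). In a single-center study of about 16 subjects, reliance on judgment is a legitimate choice.

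Much of this stands. The documents do not show that a higher cut was meant, and the judgment criteria can remove a subject with moderate impairment. What does not follow is that the criterion is sound: if the number governs, the rule admits a group that it names as excluded. An investigator who sees an explicit limit of 30 may also reasonably take a value just above it as acceptable, which weakens the judgment criteria as a backstop.

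A reader might go further and infer that the trial has no renal safeguard, or that subjects with moderate impairment will be enrolled. The documents support neither. Beyond the judgment criteria, creatinine is measured at screening and at study visits (Section 12.3.7), and an external physician safety monitor is planned (Section 13). The drug pamphlet in Appendix H is not visible, so nothing can be said about any renal dosing advice in it. The number of candidates with moderate impairment is not given.

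**Conclusion.** The point holds and should be fixed. Exclusion 9 contradicts itself: beyond the severe category, the word 'moderate' excludes no one, and subjects with moderate impairment are kept out only by judgment. This follows from the documents' own use of the number and needs no outside staging, only the premise that moderate is a milder category than severe.

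It is more than clerical because it concerns a mandatory safety limit for a renally cleared drug titrated to 2000 mg/day. Its reach is limited all the same. No estimate or test is affected, and no enrolment probability can be given. It would also be tempting to say that 30 is a slip for a higher value; the text is equally consistent with 'moderate or' being the slip, and only the sponsor can say which. Nor is this a finding about the visit schedule or the discontinuation criteria, since neither correction would change them.

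**What to change.** In both the Synopsis and Section 9.1.2, replace the cut with the upper eGFR bound of moderate impairment, so that the criterion excludes the group it names. The sponsor must state the bound; about 45 to 60 is my assumed range, not a figure from the documents. Apply it to the eGFR calculated from the screening creatinine at the pre-baseline eligibility review, both of which are already in Section 12.2.1.

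Cost: no new test or visit. A higher cut may lose a few candidates from a population that Section 9.2.1 describes as rare. Because it changes eligibility on safety grounds, it needs an amendment resubmitted to the IRB under Section 16.3.

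If the sponsor confirms that only the Section 6.4 contraindication is meant, delete 'moderate or' in both places. That is an editorial correction: it loses no candidates and changes no enrolment decision made on the number, but it leaves moderate impairment to investigator judgment, and the protocol would then say so openly.

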#### **CONFIDENTIAL INFORMATION**

The information in this study protocol is confidential. Any disclosure, copying or distribution of the information contained within is strictly prohibited without written consent from University of Florida.

13. Subject with implanted electrical device (i.e. cardiac pacemaker or a neurostimulator), metal or metallic clip(s) in their body (i.e., an aneurysm clip in the brain) that will be damaged by participation in the MRI portion of the study.
14. Anything else that, in the opinion of the investigator, would place the subject at increased risk or preclude the subject's full compliance with or completion of the study.

Inclusion in the study is entirely voluntary and subjects may withdraw at any time for any reason. Possible reasons for withdrawal could include serious adverse events, adverse events, and subject's choice. Subjects wishing to stop medication will immediately discontinue medication. Subjects who elect to discontinue medication will be asked to comply with end of study assessments (visit 4 on Table 3 - Schedule of Activities table) at a follow-up visit in an outpatient setting (to be determined by Investigator or Staff) at 14 +/- days after the last treatment Visit. Subjects who withdraw due to an adverse event will be followed whenever possible until resolution of the adverse event. It may be appropriate for the subject to return to the site 2 weeks after the subject is off study to evaluate for resolution of any adverse events and to receive further information about options for future clinical care. The Investigator will decide the course of action.

## **9.2. Study Enrollment Procedures**

The following screening procedures will be conducted on each potential subject.

- Obtain informed consent as evidenced by potential subject or subject's legally authorized representative signing an informed consent. Informed consent will be signed prior to any study-related procedures and prior to screening per protocol. Informed consent will be obtained by one of the investigators and/or his or her designee.
- Record medical history
- Documentation of disease and C9orf72 mutation
- Obtain vital signs (temperature, respiratory rate (RR), heart rate (HR), blood pressure (BP)) and weight/height.
- Collect blood and urine for clinical laboratory evaluation (hematology, chemistry, liver function tests, urinalysis) and for additional molecular studies including RAN protein assessment, and urine for pregnancy test (females of childbearing potential only). For a complete list of all tests to be performed (Section 12.3.7, *Laboratory Evaluations*.)

---

#### **CONFIDENTIAL INFORMATION**

The information in this study protocol is confidential. Any disclosure, copying or distribution of the information contained within is strictly prohibited without written consent from University of Florida.

- COVID nasal collection and testing will be completed to determine if the participant is COVID-19 negative. The results from the testing will be provided to the participant the next day when results have been placed in EPIC.
- Complete physical and neurological examinations
- ALS Functional Rating Scale – Revised (ALSFRS-R)
- Eating Assessment Tool – 10 (EAT-10)
- Functional Oral Intake Scale (FOIS)
- BDI-Fast Screen
- Collection of pretreatment AEs, if the subject is receiving Metformin pre-study
- Principal Investigator's/Sub-Investigator's review of Inclusion/Exclusion criteria and all screening results/data to assess eligibility of each potential subject
- Record/Review concomitant medications

#### **9.2.1. Subject Recruitment and Retention**

Details for recruitment procedures are provided in the protection of human subjects section. Briefly, ALS patients will be primarily identified and recruited from the University of Florida-Gainesville. Due to the rarity of the C9orf72 gene mutation, if insufficient patients are recruited, physicians at the University of Florida we are in frequent contact with physicians at other ALS centers in Florida and other parts of the US (Mayo-JAX, UF Jacksonville, Baptist Health, USF, and Miami, Johns Hopkins and Washington University) or other institutions and organizations. Generally, patients with the C9orf72 gene are well-known to their attending neurologists. The PI, co-investigators, and study coordinator will be able to work with treating neurologists at these sites to identify potential participants. C9 ALS subjects currently taking Metformin or previously prescribed Metformin may be considered. If a patient known to have the C9orf72 mutation is interested, contact information will be offered to the patient so that they can communicate with local study staff at will. We have a target recruitment schedule of only 16 patients and it is expected that there will be minimal need to reach out to other sites. All other sites, if referring patients, will ONLY BE USED FOR RECRUITMENT purposes. All recruited patients will be seen at UF Gainesville. The study will be advertised through clinicaltrials.gov and IRB approved UF listings.

#### **9.2.2. Screening Logs**

Screening logs to document reasons for ineligibility and reasons for nonparticipation of eligible subjects will be maintained to document number of subjects referred, referral source,

---

#### **CONFIDENTIAL INFORMATION**

The information in this study protocol is confidential. Any disclosure, copying or distribution of the information contained within is strictly prohibited without written consent from University of Florida.

number screened, number failed due to ineligibility or nonparticipation of eligible subjects, and reasons for ineligibility or nonparticipation of eligible subjects.

### **9.2.3. Randomization/Treatment Assignment**

Randomization is not applicable. This is an open label safety and tolerability trial.

---

## 10. DRUG PRODUCT

### 10.1. Drug Information

**Table 2 Drug Information**

Treatment	
Drug Name	Metformin SR
Strength	500mg
Dosage Form	Oral tablet
Manufacturer	
Dose	1 x 500 mg/day during week 1 2 x 500 mg/day during week 2 3 x 500 mg/day during week 3 4 x 500 mg/day during weeks 4-24 4 x 500 mg/day during Weeks 24-Week 36 (Optional dosing)

---

## **11. INVESTIGATIONAL PRODUCT**

### **11.1. Handling of Study Drug, Packaging and Labeling**

The Investigative team will obtain a sufficient quantity of the study drug from the UF Pharmacy to allow completion of this study including 10% extra for replacements if pills are lost or misplaced by study subjects.

The study drug will be sent to the Investigator. Each individual bottle with drug will be labeled in English containing at minimum: Protocol Number, Drug Name, Strength, Dose and Route of Administration, and cautionary statements required by the FDA about the use of this FDA approved drug to test the safety and tolerability of the drug in C9orf72 ALS patients, “Keep Out of Reach of Children”, storage conditions and batch/lot number.

The site pharmacy will keep a log of study drug kits received and dispensed identified by subject ID, subject initials, and date dispensed. Study drug will be stored at room temperature as directed by institutional SOP. The site pharmacist or coordinator as indicated in the delegation log will dispense study drug at the study visit #1, visit #2, visit 3 and visit 4. Subjects will begin treatment with Metformin at a dosage of 500 mg / day with an escalation of dosage by 500 mg every week to a maximal dosage of 2000 mg. Dosing will be twice daily from week 2 to week 24. In accordance with local regulatory requirements, the investigator, designated site staff, or head of the medical institution (where applicable) must document the amount of investigational product dispensed to study subjects, the amount received, and the amount destroyed upon completion of the study. The investigator is responsible for ensuring product accountability records are maintained throughout the course of the study. The inventory record will include details of Metformin study drug received and dispensed to subjects, batch, and ID numbers will be maintained by the Investigator.

At the completion of the study, all unused study drug, including spares, will be retained by the study site. An accounting must be made of any drug deliberately or accidentally destroyed.

